
ensuring child caring practices. Data on morbidity will be collected and necessary medical advice for referral to the health centre will be given equally to each group. The CNP and CNO's time will be mapped and will be asked to adopt study messages to examine the practicality. Data collection, counseling on child caring practice, food demonstration and nutrition education using IEC will be organized and supervised by project staff. It is assumed that if the intervention is successful, and once the nutritional status improves, they are likely to maintain good health. The IEC on dietary practice will be communicated to the VNMC (village nutrition management committee) members for further preventive measures. Data on cost effectiveness of the nutrition education strategies will be collected by a health economist. Data will be analyzed for change in nutritional status from moderate to mild malnutrition or normal nutrition and proportions of children continuing complementary feeding will be compared between the intensive and less intensive intervention and control groups. It is expected that the results of the study will help define the effectiveness of our nutrition education package to prevent and reduce moderate malnutrition existing in large proportion of children in setting with different geographical, and cultural and feeding practices.

KEY PERSONNEL (List names of all investigators including PI and their respective specialties)

Name	Professional Discipline/ Specialty	Role in the Project
1. [name]	Scientist, ICDDR, B	Principal Investigator
2. [name]	Director, CSD, ICDDR,B	Co-Principal Investigator
3. [name]	Senior Medical officer ICDDR, B	Co-Investigator
4. [name]	BRAC, Bangladesh	Collaborative investigator

DESCRIPTION OF THE RESEARCH PROJECT

Hypothesis to be tested:

Concisely list in order, in the space provided the hypothesis to be tested and the Specific Aims of the proposed study. Provide the scientific basis of the hypothesis, critically examining the observations leading to the formulation of the hypothesis.

Hypothesis

- a. Less intensive nutrition education including food demonstration at the community level will be equally effective as intensive nutrition education for the prevention and reduction of moderate malnutrition.
- b. The effect of less intensive nutrition education given over a period of 6 months will sustain during the following six months without any intervention.

Specific Aims:

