The village nutrition management committee will be met at the onset of the study to discuss the objectives of the study, the level and types of input and cooperation that can be mobilized will be planned. A local volunteer will be identified to work for the project selected by the village nutrition committee. Village women's group will meet to plan their time and availability for demonstration and advocacy of measures undertaken for the research projects. The proportion of activity that can be channeled through the CNP and time available for the CNP will be determined. Normally nourished 6-9 month old infants, mild and moderately malnourished children less than 2 years will be taken from the CNP registrar and GMP cards. The proportion of moderately malnourished children with growth faltering and who are receiving supplementary feeding will be excluded from the study. It is known that in health intervention, there is visit effect, where regular visits of health workers indirectly influence caregivers to ask about child's well being and seek advice. To minimize the effect all groups will receive same number of visits for information collection.

Design of the project:

This will be a prospective longitudinal intervention study. The study will have

- a) a management approach and
- b) a preventive approach.

Management approach study groups

- (1) One intervention group of moderately malnourished children without growth faltering will

receive **intensive nutrition education** (INE) and demonstration of appropriate complementary feeding at home in same intensity of recently completed study at Shahrasti thana in Chandpur district. The education will include food demonstration, specific education on diet, components of caring practices, and disease control linking to the referral system.

- (2) The second intervention group will be moderately malnourished children without growth faltering who will receive **less intensive nutrition education** (LINE) food demonstration and specific education on diet, components of caring practices, and disease control linking to the referral system.

Preventive approach study groups

- (3) The third group will be the preventive group with mildly malnourished children and well-nourished 6-9 months aged infants who will receive less intensive nutrition education same as the second group of moderately malnourished children

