As almost 80% of the 6-9 month old infants will be included in mild and moderate groups, rest 20% who are well nourished will be studied with less intensive education for preventive approach. There will be $(50 \times 2) = 100$ infants in 6-9 month old group to receive either less intensive education on complementary feeding or no education. These well nourished infants will be analyzed separately to see if less intensive education on complementary feeding prevents them from falling to mild or moderate malnutrition.

Selection and randomization procedure: (Tables 1,2,3)

For management approach the number of subjects will be 375 in each group and a total of 750 children will be selected from 40 CNCs from 4 divisions. One thana will be randomly selected from each Division, and two unions will be randomly selected from each thana, and 5 CNS will be randomly selected from each union. From a total of $(5 \times 2 \times 4) = 40$ CNCs, 20 will be allocated for intensive education and 20 will be randomly allocated for less intensive education.

To avoid contamination for the control groups with no nutrition education in the preventive approach, 8 additional CNCs will be randomly selected one from each union of the four divisions. Finally in each union 5 CNCs will be under either intensity of education and one CNC will be with no education. A diagram is given below:

LINE : Less intensive nutrition education, INE : Intensive nutrition education

Table 1

Sample selection

Subjects	Intensive education	Less intensive education	No education	Total
Moderately malnourished	375	375	---	750
Mildly malnourished	---	190	190	380
6-9 months old infants	---	50	50	100
CNCs	20	20	8	48

Table 2

RANDOMIZATION PROCEDURE

[figure not shown]
[figure not shown]

Table 3

Selection procedure

Randomization procedure:

(a) Total number recruited moderately malnourished children are 750. They will be selected equally from 40 CNC's in two study groups. Individual child will not be randomized but the children in each CNC as a group will be allocated randomly to either of the two study groups according to a random number table. Identified 5 CNC's in each union will be randomly allocated by their identification numbers to one of the two study groups.

(b) In the preventive group, mildly malnourished children will be randomized by CNCs for less intensive nutrition education or no nutrition education.

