FGD will be conducted on mothers in 6 groups each from 3 CNC's (1 control and 2 study areas). There will be 6-8 mothers of moderately malnourished children in each Focus Group Discussion. This is expected to be more or less homogenous, since mothers having young children in the villages are of similar age FGD will be conducted by the anthropologist. Moderator will play the role of guiding the group on the right topic by putting them on the track. The research personnel will facilitate discussion but they will not influence the discussion. A tape recorder will be used to record the discussion. One facilitator will take notes. Obtained data from FGD will be analyzed manually by using coding.

The FGD will be conducted again to evaluate the change in behaviour and the process indicators. The method indicated above will be followed in the later part of the study.

A pre-test on knowledge of child feeding practice will be done and will be repeated with same the questionnaire after the diet counselling sessions with the mothers. Data on feeding frequency, preparation of information on child feed, dietary ingredients, frequency of feeding and constraints will be recorded at two weekly intervals in study groups. Post test will be conducted at the end of

nutrition education period.

The health assistants will be pre-testing the nutrition knowledge of the mothers and mothers will be observed before actual training is given. These subjects will not be included into study. This will reduce observer bias of the health assistants.

Outcome variables:

1. Mothers understanding and ability to identify moderate malnutrition in children.
2. Mothers understanding on consequence of moderate malnutrition.
3. Change in knowledge of mothers in feeding practices.
4. Frequency of home feeding (Breast-feeding and supplementary feeding).
5. Frequency of seeking medical care during illness, referral, incidence, duration of illness.
6. Adequacy of child feeding, frequency & type of feeding.
7. Weight gain, weight for age and weight for height at the end of intervention.
8. Proportion of complementary feeds in 6-9 months age group.
9. Nutritional status of children at various phases of intervention and observation.
10. Adaptation level of nutrition education program by CNP, CNO.
11. Constant of not practicing education knowledge.

Secondary outcome variables: -

1. Incidence and prevalence of diarrhoea and ALRI
2. Referral success and failure
3. Resistance to education

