Data will be double entered in a microcomputer within a week of data collection. The field supervisors will visually check data before sending for entry into the computer. Any error, discrepancy or omission found during data entry will be reported to the investigators without delay. Data will be entered into microcomputer using SPSS Windows's program. Data on weight gain, frequency and introduction of complementary feeding will be compared between experimental groups. Complementary feed introduction and regularity will be compared among 6-9 month age groups in education and control groups. Comparability between intervention and control groups will be assessed by baseline characteristics such as age sex, nutritional status, socioeconomic characters, feeding practices, etc. Continuous variables will be assessed for normal distribution. T test will be performed to compare data of normal distribution; otherwise non-parametric test will be used. Chi-squared test will be performed for categorical variables, Multiple regression analysis will be done with weight gain as dependent variable and intervention and potential confounding variables such as age, sex, SES, baseline nutritional status, infection as independent variables. Separate analysis will be performed for periods of intervention, reinforcement and observation.

Compliance of nutrition education will be measured at 2 weekly observation period (already mentioned). Compliance will be measured as process indicator. Comparison of compliance will only

be done at the end of the study so that the investigators will have no idea about which group is more a less compliant. Therefore, these will be little change of introduction of bias due to non-compliance, effect of intensive or less intensive nutrition education will be compared as a whole. So complain will be seen as a factor of nutrition education with given intensive. Analysis of compliance data will be done by relating to the outcome effect of nutritional status and can be compared between two education groups.

Analysis of qualitative data

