Mother and the care givers of a child need to ensure caring the child in providing adequate feeding by appropriate breast feeding such as exclusive breast feeding up to six months of age, and continue for 2 years, provide appropriate complementary feeding after six month of age. Often, the traditional culture and food taboos pose obstacles for giving timely complementary feeding. Good complementary feeding would mean to ensure quantity and quality of feeding. Caring practice would include child stimulation by playing, and giving encouragement to the child. Giving immunization and adopting with other health care program such as vitamin A capsules and providing care for environmental health hazards. Young children frequently suffer from illnesses due to under-developed immune system. It is important to give early medical services to reduce suffering and cut the cost of diseases. In doing so appropriate referral system is to be ensured and availed. Mothers should be equipped with knowledge about the harmful effect of the diseases for child growth and mortality. Women empowerment with ability to feed the child properly and take medical care adequately is likely to ensure the caring ability of the mother. Early detection of learning disability and responding to the environment and emotional need is also essential part of caring practices.

Importance of appropriate breast-feeding practices:

It necessary to ensure exclusive breast feeding from birth to 6 months. At present, only 15% of children are exclusively breast-fed. Therefore it is a big challenge to get 100% exclusive breast-feeding. The infants should get appropriate complementary feeding from 6 months to 24 months. In this period family food need to be introduced. There is a need to caution that even children up to 24 months are rapidly growing, they are not adults, they need more than 3 times a day frequency of complementary feeding and they do not get food outside home like the adults.

Prevention of malnutrition:

The preventive approach would essentially address the determinants of malnutrition from early infancy.

Complexity of malnutrition

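### Introduction of complementary food is compared in infants enrolled at 6-9 months whatever they already eat, so starts that precede enrolment can dilute the education effect

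*Protocol*

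**What the plan says.** The Data Analysis section sets the comparison: "Complementary feed introduction and regularity will be compared among 6-9 month age groups in education and control groups". For feeding it names only two-sample tests (t test or a non-parametric test, and chi-squared). The one regression model has weight gain as its dependent variable.

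Feeding also appears elsewhere in other terms. The Outcome variables list has "Proportion of complementary feeds in 6-9 months age group" as item 8, with no time point. The Project Summary says "proportions of children continuing complementary feeding will be compared between the intensive and less intensive intervention and control groups".

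On who is enrolled, the Material and methods section says that well-nourished 6-9 month infants, with the mildly and moderately malnourished children, "will be taken from the CNP registrar and GMP cards". No feeding status is required at entry. The preventive sample-size section provides 100 "infants in 6-9 month old group to receive either less intensive education on complementary feeding or no education", 50 per group, and says, with the grades of malnutrition in mind: "These well nourished infants will be analyzed separately to see if less intensive education on complementary feeding prevents them from falling to mild or moderate". It also remarks: "As almost 80% of the 6-9 month old infants will be included in mild and moderate groups".

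On feeding in this population, Annexure 3 states: "At present, only 15% of children are exclusively breast-fed". No age or source is attached, although the sentence before it concerns birth to six months.

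**The concern.** Introduction happens once. For an infant already eating other foods at enrolment the event is in the past, and nothing taught afterwards can alter it. The plan does not define introduction, fix a time point, or say how such infants are counted. A simple comparison over all enrolled infants therefore mixes events that education could influence with events settled beforehand.

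At stake is the behaviour for which these infants were brought into the study. The Project Summary gives securing their complementary feeding as the reason for including them. A diluted comparison could make less intensive nutrition education (LINE) look ineffective on that behaviour when it is not.

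**Working it through.** **Inputs from the protocol.** 50 infants per group (preventive sample-size section, Table 1); 15% exclusively breast-fed (Annexure 3); cluster factor 1.5, which the plan applies to the moderately and mildly malnourished groups but not to these infants.

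**The plan's own figure.** The 50 x 2 = 100 infants come with no event rate, target difference or power, so there is nothing to reproduce. The plan's formula does work for its neighbours:

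- Management groups: (0.5 x 0.5 + 0.35 x 0.65) / 0.15² x 10.5 = 222.8 (stated 222).
- Mildly malnourished, assuming 50% v 30% because the rates are not legible: (0.25 + 0.21) / 0.20² x 10.5 = 120.75 (stated 121).

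**Ceiling on prior starters.** 1 - 0.15 = 0.85, and 0.85 x 50 = 42.5, so at most about 42 of 50 per group. This treats every infant who is not exclusively breast-fed as already on complementary food, so it is a bound and not an estimate.

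**Dilution.** Let s be the share already started at enrolment, and p1 and p2 the introduction rates by the end of education among the rest. Counting prior starters as introduced in both groups gives observed rates

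a = s + (1 - s)p1 and b = s + (1 - s)p2, so b - a = (1 - s)(p2 - p1).

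**Illustration.** Assume p1 = 50% and p2 = 70%; neither rate is in the documents. Power at two-sided 5% is

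Φ{[|b - a| - 1.96√(2p̄(1 - p̄)/n)] / √[(a(1 - a) + b(1 - b))/n]}, where p̄ is the mean of a and b.

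At s = 0.5, a = 0.75, b = 0.85 and n = 50: (0.10 - 1.96 x 0.080) / 0.0794 = -0.72, so power is 24%.

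Power in brackets divides n by a cluster factor of 1.5.

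| s | Observed difference, all infants | Power, 50 per group | Not yet started, per group | Power for 50% v 70% in that subset |
|---|---|---|---|---|
| 0 | 20 points | 53% (38%) | 50 | 53% (38%) |
| 0.30 | 14 points | 34% (24%) | 35 | 40% (28%) |
| 0.50 | 10 points | 24% (17%) | 25 | 30% (21%) |
| 0.70 | 6 points | 15% (11%) | 15 | 20% (14%) |
| 0.85 (ceiling) | 3 points | 9% (7%) | 7.5 | 12% (9%) |

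Restricting to infants not yet started keeps the difference at 20 points and does slightly better on power in every row below the first, but the groups become small. That is why the main comparison should be one that every infant can contribute to.

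**The case against.** The strongest reply is that the 15% figure proves little. It has no age, and an infant who is not exclusively breast-fed need not be on complementary food: Annexure 3 itself mentions diluted milk formula as a common feed. The Background section says complementary foods are started late in Bangladesh, and the Conceptual frame work section aims at introduction and maintenance of appropriate feeding, which an infant on thin milk has not reached. This stands. A reader might infer that most of these infants, up to 85%, have already started; the documents do not support that, and s could be far lower.

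A reader might also infer that the outcome cannot be scored. That is too strong. Regularity, frequency and current status can be scored in every infant, and the Data Analysis section lists feeding practices among the baseline characteristics, so prior starters can be identified. Nor do the three descriptions of feeding contradict one another; they can be read as several measures.

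A third inference is that same-age mildly malnourished infants are thrown away. The text does not say so. The comparison sentence speaks of 6-9 month age groups without restricting them to the well nourished. The separate analysis of the well-nourished infants concerns their fall into malnutrition, not feeding. The wording is ambiguous, no more.

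Finally, coding rules are often left to an analysis plan. That covers the definition of introduction. It does not cover the choice the protocol does make: a direct comparison of introduction over infants selected without regard to feeding, by tests that ignore baseline feeding.

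**Conclusion.** The concern holds in a limited form. Introduction is compared across infants of whom an unknown share started before enrolment (before enrolment, not before randomisation, since allocation is by community nutrition centre). If those infants count as introduced in both groups, a true difference is multiplied by (1 - s). The direction is certain under that scoring rule, which the plan does not state. The size cannot be derived: s is not given, 0.85 is only a loose upper bound, and the 20-point effect is assumed for illustration.

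The point touches one strand of the feeding outcomes. The nutritional-status comparisons behind both sample-size calculations, and the separate analysis of the 100 well-nourished infants, are unaffected. It is still more than a request for a definition, because a better comparison is available from data already planned.

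**What to change.** Replace the sentence on the 6-9 month groups in Data Analysis with wording such as:

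*In infants aged 6-9 months at entry, complementary feeding at the end of education (given or not, frequency and type, from the two-weekly feeding record) will be compared between LINE and no-education centres, adjusted for feeding at baseline. Introduction will be reported only among infants not yet receiving complementary food at baseline.*

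State also whether the 6-9 month age groups include mildly malnourished infants of that age. If they do, adjust for nutritional group as well. Leave in place the Project Summary's feeding comparison across intensive, less intensive and control groups, which serves a different question.

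The cost is wording and a baseline-adjusted analysis. Baseline feeding practices and two-weekly feeding data are already to be collected. The two-weekly record is described for the study groups, so confirm that it covers the no-education centres; Material and methods already gives all groups the same number of information visits. The drawback is that the introduction result rests on a smaller subset, for example 25 per group at s = 0.5, and should be read as descriptive.

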(c) Another preventive group of well-nourished 6-9 month aged infants for complementary feeding will be randomized by CNCs into either to less intensive nutrition education or no nutrition education.

Staff training:

A staff-training curriculum will be developed on the basis of the experience of the recently completed operations research at Shahrasti. A module of training manual will also be produced to fulfill the adaptation need of the CNP/CNO's with newer findings of the project. Staff training will be at Dhaka. Another training manual will be prepared for mothers according to earlier study and FGD reports.

Quantitative data collection

One health assistant (preferably graduate level having recognized ability to communicate with village mothers) will be appointed to provide nutrition education and collection of data in the area covered by 3 CNCs. There will be one supervisor with nutrition background to train the health assistants and organize and supervise nutrition education on child feeding and caring practices. Investigators will train and guide the health assistants. An anthropologist and a nutritionist will participate in counseling on child feeding and caring practices.

Anthropometric data will be collected monthly from the GMP sessions with accuracy ensured. Accuracy of weighing scales will be tested against a known weight by health assistants. The project nutritionist will also standardize the weighing method. Separate study data will be collected if the quality of anthropometry of CNPs is not acceptable. A project physician will record a base line clinical assessment of deficiency signs of micronutrients. Weight will be taken using salter scale (UK) (sensitivity 100g). Length will be measured by a locally constructed length board with precision of 1mm. Staff will be trained by Investigators and nutritionist. MUAC- data will be collected with TALC (Teaching Added at Low Cost)(UK) tape with causes of 2 mm.

Data on compliance level of nutrition education will be collected during 2 weekly observation period. Data on causes of noncompliance will be also recorded. Changes in child feeding frequency and changes in dietary composition will be recorded

Referral system and disease control

A project medical officer will educate on timely referral to Thana Health Complex (THC) or FWC during illness of the child. A communication with THC medical officer will be strengthened for BINP initiatives for malnourished children.

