Data collection on anthropometry e.g. weight, length and mid upper arm circumference was done by the health assistants at two weekly intervals, morbidity at weekly interval, food intake and feeding practices at weekly intervals on pre-designed questionnaire. Point prevalence survey was conducted to find the practices of mothers on child feeding behavior. The study subjects were followed up for observation for a period of three months in absence of intervention.

There was significant improvement in nutritional status with intensive nutrition education in three months time. The results show that the nutrition and other education reduced 56% of moderate malnutrition, supplementary feeding and nutrition education reduced 64% and there was 30% reduction in the control group.

Net weight gain (grams) over three month's of intervention was 436 Vs 320, 688 Vs 334, 910 Vs 636 grams at one month, 2 months, and 3 months of intervention in education Vs control group respectively. The weight gain in group receiving both supplementation and education was even grater, 487g at 1 month, 763g at 2 month, and 1061g at three month respectively. The rate of weight gain in 3 months was 104, 154 and 182 g/kg in control, education and SF+ education group respectively ($p < 0.001$). There was substantial improvement in complementary feeding frequency (average 5.3 from 2.5 times per day) associated with nutrition education compared with the control group.

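### A normality check chooses between t test and rank test, so feeding frequency and other continuous outcomes without a planned model could be compared with no estimated difference

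*Protocol*

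**What the plan says.** All of the following is in the protocol.

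- **Data Analysis, outcomes compared:** "Data on weight gain, frequency and introduction of complementary feeding will be compared between experimental groups".
- **Data Analysis, choice of test:** continuous variables are first checked for normality, and then "T test will be performed to compare data of normal distribution; otherwise non-parametric test will be used". The section does not say whether normality is judged by a formal test or by eye, or which rank test follows.
- **Data Analysis, model:** "Multiple regression analysis will be done with weight gain as dependent variable and intervention and potential confounding variables such as" age, sex, socioeconomic status, baseline nutritional status and infection. This does not depend on the normality result, and it is planned for weight gain only.
- **Data Analysis, categorical outcomes:** these go to a chi-squared test.
- **Outcome variables:** the list includes weight gain (item 7) and feeding frequency (items 4 and 6).
- **Quantitative data collection:** "Weight will be taken using salter scale (UK) (sensitivity 100g".
- **Selection and randomization procedure, Table 1:** whole CNCs are allocated, 20 to intensive education (INE), 20 to less intensive education (LINE) and 8 to no education. There are 375 moderately malnourished children per management arm. The preventive arms have 190 mildly malnourished children and 50 well-nourished infants each.

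**The concern.** A rule that looks at the data and then picks the test is useful only if the default test would mislead when the check fails. At several hundred children per arm, the t test's error rate hardly depends on the shape of the data. The check, however, grows more sensitive as the sample grows and reacts to coarse recording. So it is most likely to remove the comparison of means where that comparison is safe.

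What is at stake is the estimate. Feeding frequency is the behaviour that the education is meant to change. If it is sent to a rank test, the plan names no difference in feeds per day and no interval for it. For weight gain, a rank test and a mean-based regression could both be reported. They test different things, and nothing states which one governs.

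**Working it through.** **1. The plan's own figure.** The management sample size uses proportions 0.50 and 0.35:

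n = (0.5×0.5 + 0.35×0.65) / 0.15² × 10.5 = 0.4775 / 0.0225 × 10.5 = 222.8 (stated 222).

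222 × 1.5 = 333, and 333 × 1.1 = 366.3 (stated 366, taken up to 375). This reproduces. It rests on a proportion, so the t/rank rule does not touch it.

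**2. Does the t test need protecting?** Evaluable children per management arm: 375 × 0.9 = 337.5. In 4,000 simulated comparisons of Poisson counts with mean 2.5 and 375 per arm, the t test's type I error was 5.5%. The Monte Carlo standard error is √(0.05×0.95/4000) = 0.34 percentage points, so this is compatible with 5%. The infant groups of 50 per arm were not simulated.

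**3. Feeding frequency.** The pilot (Results from the initial study at Shahrasti) reports "average 5.3 from 2.5 times per day" and no SD. Assumed: whole-number feeds per day, as a rounded normal with mean 2.5 (SD 1) or 5.3 (SD 1 or 1.5), or as Poisson with mean 5.3. With n = 190, 375 and 750 and 1,000 samples per setting, Shapiro–Wilk and Lilliefors each rejected normality in 100% of samples in every setting.

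**4. Weight gain.** The protocol gives no SD. One can be backed out of the pilot:
- Three-month gain was 910 g with education. With education plus supplement the gains were "487g at 1 month, 763g at 2 month, and 1061g at three month respectively". The difference is 1061 − 910 = 151 g.
- The pilot calls this not significant at p < 0.1. Assume p lies between 0.05 and 0.10. The SE is then 151/1.96 = 77 g to 151/1.645 = 92 g.
- Assume the 282 children are the total over three groups, so 94 each. SD = SE / √(2/94), about 528 to 629 g.

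Share of samples failing normality through 100 g rounding alone, when true gain is exactly normal:

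| SD of gain | n | Shapiro–Wilk | Lilliefors |
|---|---|---|---|
| 0.3 kg | 375 | 100% | 100% |
| 0.4 kg | 375 | 84% | 100% |
| 0.6 kg | 375 | 25% | 84% |
| 0.8 kg | 375 | 12% | 56% |
| 0.6 kg | 190 | 11% | 47% |

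Whether weight gain fails therefore depends on an SD and a test that the protocol does not state.

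**5. Can the choice change the answer?** Take n = 337 per arm, SD 450 g (assumed) and a true mean difference of 100 g. If all children benefit equally, power is 82% (t) and 81% (rank). If instead 10% of children gain an extra 1,000 g, it is about 73% and 49%, and the tests disagree in 24% of trials. These runs ignore clustering. With the plan's factor of 1.5 the effective n is 337/1.5 ≈ 225 and t-test power in the equal-benefit case falls to about 65%. The figures compare the two tests and do not forecast the trial's power.

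**6. What an estimate would offer.** With 333 evaluable children per arm and cluster factor 1.5, the 95% half-width is 1.96 × SD × √(2×1.5/333) = 0.186 × SD. That is about 112 g for weight gain at SD 600 g, and 0.19 to 0.28 feeds per day at SD 1 to 1.5. It assumes that the factor 1.5 also holds for these outcomes.

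**The case against.** Four counter-arguments carry weight.

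- **A reader might infer that all the main continuous outcomes get a p-value and no size of difference.** The Data Analysis section does not support that. Its regression of weight gain on intervention is unconditional, and the intervention coefficient is an adjusted difference in grams. Nor does any text say that only p-values will be reported; a rank test can be accompanied by medians or a Hodges–Lehmann shift, and such detail is commonly left to a SAP.
- **A reader might infer that weights read to 100 g will nearly always fail.** At the pilot-implied SD, Shapiro–Wilk fails about a quarter of the time. No formal test is named, and judged by eye weight gain could well pass. Real skewness could raise the rate, but the protocol gives no data on it.
- **A reader might infer that the hypothesis that LINE "will be equally effective as intensive nutrition education for the prevention and reduction of moderate malnutrition" cannot be judged.** The sample-size section ties the management comparison to the proportion improving, which is categorical and goes to chi-squared. The switch never reaches it.
- **A rank test cannot carry CNC or baseline.** That is true, but it is equally true of a plain t test, so it is no argument against switching between them. It is an argument for a model.

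The power contrast in favour of the t test also comes from a constructed scenario; under an equal benefit the tests nearly agree. What remains is the switch itself, which the protocol fixes, and its consequence for outcomes that have no model.

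**Conclusion.** The point holds in a limited form and is minor. The protocol fixes a data-dependent choice of test that has little to protect at 337 to 375 children per arm. If normality is tested formally on whole-number counts, feeding frequency goes to a rank test with no model and no named estimate. The same applies to any other continuous outcome outside the weight-gain regression. For weight gain the remaining defect is that a rank test could stand beside the regression with no statement of which governs. The proportion improving and the sample size are unaffected.

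The conclusion on feeding frequency assumes single-occasion counts and a test such as Shapiro–Wilk or Lilliefors. Feeding data are recorded every two weeks, so an average over visits would be less coarse and might pass. All SDs used are assumed or backed out of a pilot p-value.

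**What to change.** In Data Analysis, delete the normality-dependent choice. In its place, state that each continuous outcome, weight gain and feeding frequency in particular, is reported as a difference in means with 95% confidence interval, whatever its distribution. The estimate comes from one prespecified linear model containing arm and the baseline value of the outcome.

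CNC should enter as a random effect or through cluster-robust standard errors, with a small-sample correction. The correction matters most in the preventive comparison, which has 20 CNCs against 8. CNC should not be an ordinary fixed covariate: each CNC belongs wholly to one arm, so the arm effect could not be separated from the CNC effects.

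Keep the rank test only as a sensitivity check, and say that the model governs.

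The cost is wording; the data collected do not change. The small downside is that a mean difference describes a strongly skewed outcome less well, which the sensitivity check covers.
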